month prior to implementation, we will train home visitors and mental health professionals on MB. We will stagger implementation in two waves so that only half the sites are implementing at once. This will allow our Intervention Coordinator to focus her efforts on ensuring attendance at intervention groups and fidelity to intervention protocols. Study recruitment and implementation of all prenatal MB sessions will be completed by the 4th quarter of Year 2. This recruitment schedule will allow us to complete all postnatal MB sessions and follow-up data collection by the middle of Year 3, allowing study investigators to analyze data and prepare to disseminate study findings to both academic and community stakeholders.

Participant Screening: Participants will initially be screened for eligibility criteria by their home visiting program sites. Upon permission from the potential study participant, program sites will fill out a referral form, which will include the potential study participants name and contact information, and send it to the research team. Once the program sites refer potential study participants, a member of the study team will call the participant using the “Phone Script for Referrals” to screen the potential study participant for eligibility criteria and move forward with the consent process either via telephone or REDCap survey link.

Participant Outcomes Surveys: Participant outcomes will be collected at four time points—baseline, post-intervention, 12 weeks postpartum, and 24 weeks postpartum. Participants will receive \$20 remuneration at the baseline, 12-week and 24-week assessments. The MMS and EPDS will be administered to all clients during their baseline surveys. This information will be used for data analytics but not as an exclusion criteria. Data will only be collected from study participants who have consented to participate in the study.

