For our **non-inferiority (NI) analyses** (Aim 2) comparing MB led by home visitors vs. MB led by mental health clinicians, we used similar assumptions of a 6.0 SD on the QIDS-16. We will have >85% power to detect a difference in mean QIDS-16 scores of two points between the two arms with 1224 analyzable participants' data (i.e., 612 in each arm, or 18 clusters in each group with 34 participants on average) with an ICC no larger than .01. We have taken into consideration the potential loss of up to two clusters in each study arm for our NI analyses. Even with a loss of two clusters, which would leave us with 1064 analyzable participants' data (i.e., 532 in each arm), we will have >80% power to detect a difference in mean QIDS-16 scores of two points between study arms with an ICC no larger than .01. Since we recognize that power to claim NI will depend heavily on the magnitude of any ICC, we will perform several ICC calculations within each arm to assess power assumptions post hoc. We do not anticipate adequate power to claim NI regarding the incidence of new cases of major depression. If we assume 15% incidence in the professional arm versus 20% in the paraprofessional arm (i.e., a margin of NI of 5%), a sample size of 1224 participants would have 64% power and a sample size of 1064 would have >50% power at the 5% level of significance without accounting for any ICC. Thus, we will statistically compare the two arms with respect to MDD incidence, but do not anticipate the ability to claim NI.

15.0 Data Monitoring Plan to Ensure the Safety of Participants:

Any study participant who endorses thoughts of self-harm will be referred to the supervisor at the home visiting program, by the study coordinator. The supervisor, who is trained in responding to and addressing suicidal ideation, will use their agency's protocol to make a determination regarding whether the study participant is in danger of harming herself or others and will determine necessary steps to ensure the safety of the study participant. The Principal Investigator will be notified

immediately of any such referrals made by study staff. In addition, should administration of depression scale indicate the participant is experiencing severe depressive symptoms, the supervisor at the home visiting program will be notified in order to provide appropriate referrals for their client's mental health treatment linkage.

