Specific Aim #2 is to conduct a non-inferiority trial that compares the effectiveness of MB delivered by (a) mental health clinicians versus (b) paraprofessional home visitors.

Specific Aim #3 is to evaluate whether effectiveness of the two versions of MB (clinician led vs. paraprofessional home visitor led) varies according to patient characteristics (e.g., race, ethnicity, first-time mother, and/or geographic type of home visiting (HV) program (i.e., urban vs. rural).

Specific Aim #4 is to examine the feasibility and acceptability of MB delivered by paraprofessional home visitors and mental health clinicians.

Study time points include: baseline, immediately following the intervention period (or roughly eight weeks post enrollment for controls), 12 weeks postpartum, and 24 weeks postpartum. Primary time point of interest will be 24 weeks postpartum. This analysis plan will focus on the primary results manuscript, and thus, we will focus on Aims #1-#3.

Study Outcomes

Primary Outcome

Primary outcome of interest for Aims #1-#3 will be the Quick Inventory of Depressive Symptoms (QIDS-SR16) score as determined by participant self-report at 24 weeks postpartum. We will control for baseline QIDS-SR16 score. This is a continuous measure ranging from zero to 27 points, where higher scores signify increased depressive symptoms. QIDS-SR16 translates into depressive categories such that a score of less than five points indicates no depression, a score ranging from six to 10 indicates mild depression, 11-15 signifies moderate depression, 16-20

indicates severe depression, and anything above 20 would be labeled as very severe (<http://www.ids-qids.org/>). As a result, we deem a five-unit change or difference in score to be meaningful (as a jump in five points would result in an increase in depression severity tier for any individual patient).

Secondary Outcomes

The following secondary outcomes will further be examined in order to address subcomponents of specific aims and also to address some of the exploratory aims. These secondary outcomes align with key components of the Mothers and Babies intervention.

1. Incidence of major/clinical depression (major depressive episode [MDE])
 - a. A major depressive episode will be defined via the Maternal Mood Screener
 - b. MDE for the purposes of this study is defined as:
 - i. The participant indicates at least **five** of the problems listed within the past two weeks (part B on the form), **and**

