 - ii. **At least one** of the problems must be: symptom 1 (feeling depressed) or symptom 2 (losing interest or pleasure), **and**
 - iii. The participant indicates '**yes**' to the question: *Did these problems interfere with your life or activities a lot?*
2. Behavioral activation scale score (BA)
3. Social support (due to the highly skewed nature of this outcome, we dichotomized it into ≥ 4 versus <4).
4. Mood regulation
5. Decentering
6. Mental health service utilization (i.e., an indicator for whether participants are enrolled in therapy with a counselor and/or currently taking antidepressants). This outcome may be explored in greater detail in a separate paper; however, we plan to examine the difference between arms controlling for baseline mental health service utilization.

Tertiary Outcomes (the following will be explored in a separate paper from the primary results)

1. Pleasant activities
2. Perceived stress
3. Parental cognitions and conduct toward the infant scale
4. Dyadic adjustment scale
5. Flourishing scale
6. Prenatal health behaviors

The outcomes above are tied to validated scales with specific scoring requirements. The scoring instructions will be followed and analyses will proceed on the final, scored variables. In addition, we plan to summarize '**dosage**' of intervention in the active intervention arms as the number of sessions attended (out of six possible). We will also summarize the number of participants that were '**compliant**', which is defined as attending **at least four of the six sessions**.

Demographics and Baseline Assessments

The following are specific demographic/baseline assessments of interest for analyses. Primary analyses will adjust for these covariates as we anticipate they will influence outcome. We plan to report both adjusted and unadjusted intervention effect estimates:

1. Race/ethnicity (at the participant level): minority vs. not belonging to a minority category.
2. Whether participant is a first-time mother (i.e., current number of children = 0 at baseline).
3. Currently at risk for depressive episode (i.e., those NOT meeting criteria for MDE at baseline).

4. Primary language of intervention receipt (for MH and HV arms) or primary language in which the participant completed assessments (for control arm).
5. Education: at least some college vs. less than college.

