Analyses will proceed at the participant level. Primary analyses for QIDS-SR16 score at 24 weeks postpartum will involve all the participants in the study contributing data at this time point. Primary analyses will involve a linear mixed model for continuous outcome with independent fixed effect variables of baseline QIDS-SR16, study arm (three-level factor), and the baseline covariates listed above. We will report both covariate-adjusted and unadjusted estimates for intervention effect. Secondary analysis will be performed on those participants considered at risk at baseline (i.e., excluding the participants who do not meet the criteria for MDE as defined above). We plan to account for clustering effects via inclusion of a random site effect, which will allow for distinction of between and within-site variance. We will also explore inclusion of a random 'facilitator' effect as it is possible participants exposed to the same facilitator may have correlated responses. Intra-cluster correlation coefficients will be estimated via variance components estimates.

Intervention effect will first be evaluated via the adjusted Wald type III test for significant study arm effect at the 5% level of significance. If arm is significant at the 5% level, analyses evaluating the **superiority (Aim #1)** of HV-led intervention vs. control will proceed with Tukey's correction for multiple pairwise hypothesis tests. Assuming the Tukey-adjusted p-value for this comparison falls below the 5% level of significance in favor of the HV-led arm, **non-inferiority (Aim #2)** will further be assessed (using Tukey's correction) via pairwise comparison of adjusted 24-month QIDS in HV-led vs. MH-led arms. Figure 1 below depicts the margin and zone of non-inferiority for this comparison.

[figure not shown]

Figure 1. Margin of Non-inferiority (NI)

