The double-sided arrows represent 95% confidence intervals for the model-estimated adjusted mean 24-week difference in QIDS-SR16 score. Note that higher score signifies more depressive symptoms; thus if the estimated difference (HV minus MH score) is larger than zero, the HV arm has on average worse depressive symptoms. Since the pre-specified margin of non-inferiority is two units on the QIDS-SR16 scale, we will claim non-inferiority if the upper limit of the adjusted 95% confidence interval for the HV-led arm minus the MH-led arm comparison remains below two. The red arrows indicate scenarios in which we cannot claim non-inferiority and the blue arrows indicate scenarios in which the criterion for non-inferiority is met.

Using the same analytic approach, we will explore the addition of covariate-by-arm interaction terms in the aforementioned model or a three-way covariate-by-arm-by-time interaction term in the longitudinal modelling in order to explore whether effectiveness of intervention varies by patient characteristics (Aim #3). The covariates to be explored include: race/ethnicity, first-time mother, language, education, and use of mental health services at baseline. These analyses are more exploratory in nature, and thus power/sample size considerations do not focus on interaction effects. As a result, we anticipate evaluating interaction effects at the 10% level of significance without adjustment for multiple hypothesis tests. Qualitative data analysis methods will evaluate feasibility and acceptability of MB in each setting (Aim #4), and the details of these analyses will be specified elsewhere.

Additional analyses surrounding Aims #1-#3 will employ longitudinal methods, utilizing all study data at all time points (i.e., inclusion of a fixed study time point effect). Secondary outcomes will all be analyzed in this fashion with the exception being binary response variables (e.g., depression onset). In these cases, appropriate link and distributional assumptions (logit, binomial, respectively) will be specified. For the participants receiving active intervention (either HV-led or MH-led Mothers and Babies), we will examine a 'dose' variable in relation to outcomes. This dose variable will be defined as the number of sessions (out of six possible) attended for an individual participant.

Analytic Dataset

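### The rule for the secondary at-risk analysis is inverted: read literally, it keeps only women already in a major depressive episode

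*SAP*

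**What the plan says.** The SAP uses the term *at risk* in two places that matter here.

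- **Demographics and Baseline Assessments, item 3** lists it as an adjustment covariate and defines it: "Currently at risk for depressive episode (i.e., those NOT meeting criteria for MDE at baseline".
- **Statistical Methods**, in the paragraph that sets out the QIDS-SR16 model, restricts a secondary analysis to at-risk women and explains the restriction: "Secondary analysis will be performed on those participants considered at risk at baseline (i.e., excluding the participants who do not meet the criteria for MDE".

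MDE itself is defined under Secondary Outcomes: "A major depressive episode will be defined via the Maternal Mood Screener". It requires at least five problems in the past two weeks, at least one of two core symptoms, and substantial interference with life or activities.

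The protocol (section 4.0, Participant Outcomes Surveys) administers this screener and the EPDS to all clients at baseline and says of the results: "This information will be used for data analytics but not as an exclusion criteria". Women with and without a current episode can therefore both be enrolled, and the SAP's shell for the baseline table has a row for meeting MDE criteria.

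The primary model's fixed effects are baseline QIDS-SR16, "study arm (three-level factor), and the baseline covariates listed above". That covariate list includes the at-risk indicator.

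**The concern.** The parenthesis is the operative rule, the part a programmer would code. It contains a double negative: it excludes those who do *not* meet the criteria. The result is the opposite of the population that the label names and that the covariate list defines.

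For a preventive intervention this reverses the meaning of the result. Women without a current episode are those in whom onset can be prevented. Women already in one can only improve, persist or worsen. An estimate from the second group, published under a label that means the first, would mislead readers. If the analyst instead corrects the rule silently, a choice between two opposite populations goes unrecorded, although the SAP's Technical Details section expects changes to the analysis to be documented in the SAP.

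**Working it through.** **Step 1. Apply both rules to each baseline status.** The plan gives no size for this subset, so there is no figure to reproduce. The check is logical.

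| MDE at baseline | At risk under covariate item 3? | Kept under the Statistical Methods rule? |
|---|---|---|
| Yes | No | Yes |
| No | Yes | No |

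The two sets do not overlap, and together they cover every woman whose baseline screener can be classified. Women with no usable baseline screener belong clearly to neither.

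**Step 2. Look for a reading that rescues the rule.** The full parenthesis is "i.e., excluding the participants who do not meet the criteria for MDE as defined above". The reference back is to the MDE criteria under Secondary Outcomes, which do not undo the double negative. The protocol (section 3.0) also describes the whole study population as at risk for major depression, but that sense would exclude no one and cannot be what is meant. The rest of the plan fits the covariate definition. The protocol's stated purpose (section 1.0) is prevention of onset and worsening, its power analysis (section 14.0) speaks of power "regarding the incidence of new cases of major depression", and the SAP's secondary-outcome text refers to "the exception being binary response variables (e.g., depression onset". Nothing in either document supports a subset made up only of women in an episode.

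**Step 3. Illustrate the size.** Inputs:

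- sites contributing data: 15 HV, 16 MH, 6 control, 37 in all (SAP, Randomization Methods);
- 23 analysable women per site on average (SAP, Power and Sample Size Considerations, where it was planned for 38 sites);
- baseline MDE prevalence *p*: not in the documents, so assumed.

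Analysable women: 15 × 23 + 16 × 23 + 6 × 23 = 345 + 368 + 138 = 851. The written rule keeps 851 × *p*; the SAP's definition keeps 851 × (1 − *p*).

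| Assumed *p* | Written rule: total (HV / MH / control) | SAP definition: total (HV / MH / control) |
|---|---|---|
| 10% | 85.1 (34.5 / 36.8 / 13.8) | 765.9 (310.5 / 331.2 / 124.2) |
| 20% | 170.2 (69.0 / 73.6 / 27.6) | 680.8 (276.0 / 294.4 / 110.4) |

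Over a wider range of 5% to 30%, the written rule keeps about 43 to 255 women and the definition about 808 to 596.

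**Step 4. Check the covariate list in the subset.** The sentence sits in the QIDS-SR16 paragraph, so it most naturally means that model rerun in fewer women. Take the columns intercept, two arm indicators, baseline QIDS and the at-risk indicator. In all women these five columns are linearly independent (rank 5). In either subset the at-risk indicator has a single value, so it is a multiple of the intercept or zero, and the rank is 4. Its coefficient cannot be estimated there under either wording.

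**The case against.** The strongest reply is that this is a drafting slip that the SAP corrects itself. The sentence names its population by a label, and the covariate list defines that label with a capitalised negative. An analyst who codes from the covariate would pick the right women. No decision rule or multiplicity step uses the subset, and it does not appear in the Analytic Dataset section, the power section or the table shells. All of this is true, and it limits the consequence to one secondary analysis. It does not make the text right: the written rule and the definition still select opposite women.

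Three lesser points also stand in part:

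- The constant covariate is incidental. The SAP does not state a covariate set for this subset, and dropping a constant column leaves the arm contrasts unchanged. It is no evidence of the inversion, because it arises under the correct wording too.
- The counts rest on an assumed prevalence and on a planning average spread evenly over sites, although the SAP expects uneven recruitment. They should not be read as estimates. The zero overlap needs none of them.
- The sets are complements only among women with a classifiable baseline screener, and the SAP does anticipate some missing baseline data.

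**Conclusion.** The concern holds. The rule in Statistical Methods selects women with MDE at baseline; the SAP's definition of *at risk* selects women without it. The overlap is zero at any prevalence among women with known baseline status, and that conclusion rests on the wording alone. The counts, about 85–170 women instead of about 681–766, are an illustration that depends on an assumed 10–20% prevalence and 23 analysable women at each of 37 sites.

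The effect is confined to one secondary analysis. The intent can be recovered from the label and the covariate definition, but the written rule should be corrected before the analysis is run.

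**What to change.** In SAP, Statistical Methods, reword the parenthesis so that the secondary analysis excludes women who *do* meet MDE criteria at baseline, in agreement with item 3 of Demographics and Baseline Assessments. State that the at-risk covariate is left out of that subset model because it is constant there. It would also help to say how women with no usable baseline screener are classified.

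The cost is a one-line correction and one covariate removed from one model. No new data are needed, since the screener is already given at baseline. The documents give no database lock date; the correction should be recorded as a dated SAP change, in keeping with the SAP's own version control.

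A separate matter, which does not follow from this slip, is who counts in the denominator for MDE incidence. The SAP does not say, and its Table 2 shell shows a baseline row under that outcome, so the point is open and could be clarified in the same revision.

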4. Of those that meet acceptable levels of imbalance, we randomly select one allocation for use in the current study.

We chose the p-value corresponding to the Kruskal-Wallis test (nonparametric version of an Analysis of Variance [ANOVA]) as our criterion for 'balance' in step #3 above. If the p-value for each of the three variables is larger than 0.30 for a given simulated allocation scheme, that particular allocation is deemed 'acceptable'. This criterion is adapted from the 'Minimal Sufficient Balance' principle from Zhao et al. [3] in the individual sequential randomization literature.

In the current study, randomization occurred in three waves for logistical purposes. The first included 14 sites (2 C:6 HV:6 MH); the second included 19 sites (4 C:7 MH:8 HV); allocation ratio was slightly off in this wave to account for dropout sites); and the third wave included 12 sites (1 C:6 MH:5 HV). Thus, we randomized a total of 45 sites in three waves; randomization of 42 sites was the study goal, reflected in our approved research plan. However, to account for site dropping out in the meantime, we adapted the algorithm to increase the number of sites randomized and also to allow for slightly discrepant allocation ratios than the planned 1:3:3 within each wave.

After randomization, eight programs dropped out, thereby yielding a total of 37 study sites contributing data for analyses. Data collected from all study participants will be used in the analysis. Among the 37 active study sites, 16 HV programs received the MB intervention delivered by mental health professionals, 15 received MB intervention delivered by HV paraprofessionals, and six programs serve as control sites. As an aside, 29 intervention sites ended up implementing at least one cohort (15 MH, 14 HV).

Statistical Methods

Descriptive statistics will summarize baseline characteristics (both site-level and participant-level) overall and by arm. As appropriate, mean \pm standard deviation (or median [inner quartile range]) will be used in cases of skewed or non-normal empirical distributions) and frequency (proportions) will summarize continuous and categorical data, respectively. Analyses will employ normal theory methodology as appropriate, and in cases of violations of assumptions, transformations and/or nonparametric analyses may be utilized.

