We initially planned to conservatively enroll 42 sites (six controls, 18 HV-led, 18 MH-led) with a target enrollment of 40 participants per site (1680 total participants). As in any cluster-randomized trial, power and sample size considerations depend heavily on intra-cluster correlation coefficient (ICC) estimates. In general, it is recommended that these calculations account for anticipated ICC as failure to do so in the design phase and lead to an increase in type II error (i.e., result in underpowered studies) [4, 5]. Without previous knowledge of ICC(s) in this population with respect to our primary outcome, we explored a range of ICCs (0.001 to 0.05). Power calculations assume a standard deviation in primary outcome of approximately six points (on the QIDS-SR16), with a meaningful difference corresponding to five points on average across arms. Thus, for the superiority aim, we calculated power based on the average ability to detect at least a five-point mean difference between control sites and HV-led sites. Power calculations assumed a $5\%/3 = 1.7\%$ level of significance in order to account for three pairwise comparisons. This is an approach that we deem conservative as this mirrors the Bonferroni correction for multiple hypothesis tests.

We have 38 active sites: six control, 16 paraprofessional home visitor-led sites, and 16 MHP-led sites. We plan to recruit an average of 27 participants per site, allowing for up to 15% attrition (i.e., 23 participants on average for analyses). These assumptions allow for more than 95% power to detect a mean difference of five points in QIDS-SR16 across arms for an ICC of 0.01. Even if one of the six sites drops out, and if ICC is as large as 0.05 (which we deem unlikely), we still anticipate over 85% power for analyses addressing the efficacy aim (Aim #1).

Power for the NI aim will require ability to detect a smaller (margin of NI of two points) mean difference across arms. We anticipate over 90% power to detect a margin of NI of two points on the QIDS-SR16 scale if we assume an ICC of 0.01 and 16 sites in each of the intervention arms with 23 participants for analyses, on average, per site. This allows for up to 15% attrition overall. We anticipate some sites to be over/underperforming and thus unequal representation per site is inevitable. Our hope is that the precautions taken with respect to the randomization algorithm that

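### Tukey for three pairs is stacked on two aims already tested in fixed order, making the non-inferiority interval 1.21 times as wide as needed; the ICC limit and site count in the power section also need correcting

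*SAP*

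**What the plan says.** **Testing scheme (SAP, Statistical Methods).** There are three layers.

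1. An overall test of the three-level arm factor: "Intervention effect will first be evaluated via the adjusted Wald type III test for significant study arm effect at the 5% level of significance".
2. If that is significant, HV-led versus control with Tukey's correction.
3. Non-inferiority of HV-led to MH-led, again with Tukey's correction, under the condition "Assuming the Tukey-adjusted p-value for this comparison falls below the 5% level of significance in favor of the HV-led arm".

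The decision rule is "we will claim non-inferiority if the upper limit of the adjusted 95% confidence interval for the HV-led arm minus the MH-led arm comparison" stays below the margin of 2 QIDS-SR16 points. The sentence that sets up this comparison names the endpoint as "adjusted 24-month QIDS in HV-led vs. MH-led arms", although the primary time point everywhere else is 24 weeks postpartum.

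**Which comparisons matter.** Aims 1 and 2 name HV-led versus control and HV-led versus MH-led. No aim names MH-led versus control. The results shell, which the SAP calls non-binding, has contrast columns only for the first two.

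**Power (SAP, Power and Sample Size Considerations).** Calculations use 5%/3 = 1.7%, described as the "level of significance in order to account for three pairwise comparisons", and the SAP calls this conservative. Non-inferiority power is put at over 90% for ICC 0.01 with "16 sites in each of the intervention arms with 23 participants for analyses, on average, per site". The text then says the projected sample falls short of 90% if the ICC exceeds 0.02.

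**Site count.** The power section states: "We have 38 active sites: six control, 16 paraprofessional home visitor-led sites, and 16 MHP-led sites". Randomization Methods reports 37 sites after eight of 45 dropped out, with 16 MH-led sites, and adds that "15 received MB intervention delivered by HV paraprofessionals, and six programs serve as control sites".

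**The concern.** When two hypotheses are tested in a fixed order and the second is opened only by success on the first, each can be tested at the full level. If the first null hypothesis is true, any false claim requires a false rejection at step 1. If it is false, the only possible false claim is at step 2. Either way the familywise error is bounded by the level of a single test. Tukey's correction protects a family of three pairs, one of which the trial does not plan to claim. Near the margin, an HV arm that is truly non-inferior could therefore fail only because of a correction that the ordering makes unnecessary. Non-inferiority is the result meant to inform whether programs can use paraprofessionals.

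The power text raises a different problem. A reader would take 90% non-inferiority power as safe up to ICC 0.02, and Table 1 contradicts this. The two site counts cannot both be current.

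**Working it through.** **Inputs from the SAP.** SD 6, margin 2, 23 analysable women per site (27 recruited, 15% attrition), expected ICC no larger than 0.01, range explored 0.001 to 0.05. Sites: 6 control, 15 HV, 16 MH (Randomization Methods) or 6/16/16 (power section).

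**Formulas.** With m women per site, design effect DE = 1 + (m − 1) × ICC and SE = 6 × √[(DE/m)(1/k₁ + 1/k₂)]. Power comes from the noncentral t with noncentrality 2/SE and a true HV−MH difference of zero unless stated.

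**Reproducing the plan's own table.** With two-sided alpha 0.017 and df = k₁ + k₂ − 2, the women needed per site for 90% power at ICC 0.001, 0.01, 0.02, 0.03, 0.04 and 0.05 are:

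- 16+16 sites: 17, 20, 25, 33, 49, 97
- 15+15 sites: 19, 22, 28, 38, 62, 168

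All 12 entries match Table 1. The same method gives 93.4% at ICC 0.01 with 16+16 sites and 23 per site, which agrees with the stated figure of over 90%.

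**The ICC limit, by that method, at 23 per site.**

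| Sites (HV/MH) | Power at ICC 0.01 | Power at ICC 0.02 | ICC at which power falls to 90% |
|---|---|---|---|
| 16/16 | 93.4% | 88.5% | 0.017 |
| 15/16 | 92.5% | 87.2% | 0.015 |
| 15/15 | 91.5% | 85.8% | 0.013 |

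At ICC 0.02, 25 women per site are needed with 16/16 sites and 26 with 15/16. The shortfall therefore already exists at 0.02. The claim of over 90% at ICC 0.01 survives the lost HV site.

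**Cost of Tukey.** The SAP gives no df method, so I assume 37 sites − 3 arms = 34.

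- Tukey critical value q(0.95; 3, 34)/√2 = 2.450, a per-comparison level of 1.96%.
- Ordinary t(0.975; 34) = 2.032.
- Ratio 2.450/2.032 = 1.206.

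At ICC 0.01 with 15/16 sites, DE = 1 + 22 × 0.01 = 1.22 and SE = 6 × √[(1.22/23)(1/15 + 1/16)] = 0.497. The half-widths are 2.450 × 0.497 = 1.22 and 2.032 × 0.497 = 1.01. The largest observed HV−MH difference that still passes is 2 − 1.22 = 0.78 with Tukey and 2 − 1.01 = 0.99 without.

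| Scenario (15/16 sites, 23 per site) | NI power, Tukey | NI power, fixed order |
|---|---|---|
| ICC 0.01 | 93.7% | 97.4% |
| ICC 0.02 | 88.9% | 95.0% |
| ICC 0.03 | 83.6% | 91.8% |
| ICC 0.05 | 72.9% | 84.7% |
| ICC 0.01, baseline correlation 0.5 (assumed) | 98.3% | 99.5% |
| ICC 0.02, baseline correlation 0.5 (assumed) | 96.2% | 98.6% |
| ICC 0.01, HV truly 0.5 points worse (assumed) | 71.4% | 83.5% |

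The first four rows and the last take no credit for baseline adjustment. The correlation rows multiply SE by √(1 − 0.5²).

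The ICC at which power falls to 90% with 15/16 sites is 0.018 with Tukey and 0.035 in fixed order. With 16/16 sites it is 0.020 and 0.038.

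**Error rates, by simulation on site means (6/15/16 sites, ICC 0.01).** When HV is truly 2 points worse than MH and superiority over control is real, false non-inferiority is about 1.0% under the SAP scheme and 2.5% with the unadjusted fixed order. The latter is the nominal one-sided level.

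**Aim 1 and the overall test.** At the SAP's 5-point effect, Aim 1 power exceeds 99.9% with either critical value, even at ICC 0.05. For an assumed true benefit of 2 points at ICC 0.01, the overall test costs little on top of Tukey (69.9% versus 70.6%). If only Tukey were dropped, the overall test would bind (76.2% versus 82.9%).

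**The case against.** The SAP's scheme is valid, openly declared and budgeted for: the power section uses 5%/3, calls it conservative, and meets its own target of over 90% at ICC 0.01. All of this stands, and it is why the first part is a matter of efficiency.

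The headline gap ignores the planned adjustment for baseline QIDS. At an assumed correlation of 0.5 it shrinks to 98.3% versus 99.5%. The larger gaps need an ICC above what the SAP expects, or a true HV deficit. The 34 df is also an assumption: with large-sample critical values the ratio is 1.20 and power is 95.4% versus 98.1%. These points limit the size of the effect but do not change its direction.

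Relaxing a non-inferiority criterion late deserves care. The SAP already reports final site dropout, and the change raises the false non-inferiority rate. It also gives up a multiplicity-adjusted MH-led versus control comparison, which helps show that the comparator worked in this trial. These are real costs, and keeping Tukey is defensible.

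On the ICC limit, one can say that falling short above 0.02 is literally true and does not promise 90% at 0.02. The sentence still implies a limit, and Table 1 shows it lies lower. Tukey with 16/16 sites does give 0.020, but that is neither the power section's method nor the reported HV site count. The effect of the site-count mismatch is small: 93.4% becomes 92.5% at ICC 0.01.

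**Conclusion.** The concern holds, in two parts of different weight.

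The power section is wrong as written. By the SAP's own method, 23 women per site keep 90% non-inferiority power only up to ICC 0.017 (16/16 sites) or 0.015 (15/16 sites), and the counts of 38 and 37 sites contradict each other. This rests only on figures in the SAP.

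Tukey on top of the fixed order is unnecessary for the two stated aims. It widens the non-inferiority interval by a factor of 1.21 and costs about 4 points of power at ICC 0.01 and about 12 points at ICC 0.05, assuming SD 6, no gain from baseline adjustment, equal site sizes and 34 df. The cost is small at the design case. Aim 1 is essentially unaffected at a 5-point effect.

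**What to change.** **Needed whichever method is kept.** Restate power for the 37 sites (6 control, 15 HV, 16 MH), or explain why 38 is current. Replace the 0.02 limit with the one for the method kept. At 15/16 sites and 23 per site, that is about 0.015 (5%/3), 0.018 (Tukey) or 0.035 (fixed order at 5%). Correct the 24-month reference to 24 weeks. This costs nothing.

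**Optional.** Rewrite the testing rule as two steps:

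1. HV-led versus control at two-sided 5%.
2. Only if step 1 is significant in favour of HV-led, claim non-inferiority when the upper limit of the ordinary two-sided 95% confidence interval for HV-led minus MH-led at 24 weeks is below 2.

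Make the overall arm test and MH-led versus control descriptive. Remove the overall test as a gate at the same time as Tukey, because it would otherwise become the binding constraint for smaller effects. State that the adjusted interval means covariate-adjusted only, and align the alpha in the power section and Table 1.

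The optional change needs only SAP wording, but it must be documented and dated before any by-arm analysis. Timeline for Analyses bars by-arm summaries until the final analyses except for quality control, and the documents give no lock date. The price is the rise in false non-inferiority from about 1.0% to the nominal 2.5% one-sided, and no multiplicity-adjusted claim for MH-led versus control.
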